## 7.2 Efficacy

All patients enrolled in the study are to be evaluated for disease activity as outlined in the Schedule of Assessments (Table 1). Screening/baseline tumor assessments should include CT or MRI of the chest, abdomen, and pelvis, whole body bone scan, MRI of the brain and evaluation of any superficial lesions. On-study assessments will include all known and suspected sites of disease and will be performed at 8 week intervals until approximately 1-year and then every 12 weeks. The allowable windows for assessments are 4 weeks prior to first study treatment for screening/baseline assessments and  $\pm 10$  days for on-study disease assessments.

CT scans should be performed with contrast agents unless contraindicated for medical reasons. If intravenous contrast is medically contraindicated, the imaging modality to be used (either CT without contrast or MRI) should be the modality which best evaluates the disease, and the choice should be determined by the investigator in conjunction with the local radiologist. Depending on the adequacy for evaluation of disease, a combination of CT without contrast and MRI should most often be used. CT without contrast is preferred for evaluation of lesions in lung parenchyma. MRI is not adequate for evaluation of lung parenchyma but should also be performed to evaluate all other aspects of the chest. MRI of the abdomen and pelvis should substitute for CT with contrast unless the method does not adequately depict the individual's disease, in which case CT without contrast is preferred. For those sites that routinely use PET scans for assessment of bone lesions in lieu of skeletal scintigraphy, PET scans may be used on-study, with the same modality planned throughout the study for any given patient.

For patients having effusions or ascites, cytological proof of malignancy should be obtained prior to selection of the effusion as a non-target lesion. Effusions that have not been evaluated using cytology or were found to be non-malignant should not be considered to be cancer lesions.

Disease response will be assessed in accordance with RECIST 1.1 (Eisenhauer-2009). Appendix 5 provides guidance in using the response criteria and include a modification to RECIST 1.1 to address potential temporary treatment effects such as tumor lesion cavitation or flare response. Assessments will be performed until objective disease progression is documented by the investigator, or subsequent anti-cancer therapy is begun.

Patients experiencing tumor response (Partial Response [PR] or Complete Response [CR]) should undergo confirmatory assessment at least 4 weeks after initial documentation of response. It is acceptable to perform confirmatory assessments at the next appointed evaluation per protocol. Bone scan is required as an element of the confirmation of PR or CR if bone lesions were identified at the baseline assessment.

The investigator's assessment of disease response and progression will be the basis for patient management and study expansion decision making. Potential exists for individual tumor lesions to cavitate or become otherwise difficult to evaluate for a period of time as the result of beneficial study treatment impact. For example, tumor necrosis and cavitation may result in minor increase in overall individual lesion size or unclear tumor margins prior to recovery to a smaller lesion, development of scar tissue, or complete resolution. For this reason, investigators may delay reaching the conclusion of disease progression until subsequent on-study disease assessments are performed.

Central radiology review to assess RECIST outcome may be undertaken after Stage 1 of the study. Materials to be forwarded for independent review will be all imaging studies performed at screening and on study, preferably in digital format, using an electronic transfer through a portal to the review vendor or transfer on compact disc or optical disc. All digital media must be in DICOM format. Films may be forwarded for review if necessary; all films should be originals (second original films acceptable) rather than copies of films.

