The populations included in Cohorts 3 and 4, who have had progression of disease during treatment with a checkpoint inhibitor, represent a potential unmet medical need. For this reason, if results in Stage 2 of enrollment are of high interest, enrollment may be expanded to as many as 100 patients total in each cohort to narrow the 95% Confidence Interval (CI) around the ORR point estimate and more fully characterize the secondary endpoints in the population of interest.

In order to be part of the clinical activity evaluable population, the patient must have at least one on-study disease assessment or discontinue from treatment for PD prior to this assessment. Patients who discontinue treatment prior to the first on-study disease assessment for an AE, toxicity, or withdraw consent are considered non-evaluable for disease assessment. These patients will not be part of the clinical activity evaluable population.

Disease response and progression as documented by the investigator in the CRF will be the basis for patient management and study expansion decision making. Unconfirmed objective responses recorded in the CRF may be used as the initial basis for expansion of study enrollment; however, follow-up evaluations on patients with unconfirmed responses must continue to support the decision to continue to the full number of patients to be included in the next stage. Central radiology review for disease response and progression may be added to the study during Stage 2. If this occurs, central review of all radiologic assessments performed in the study will be expected (including retrospective review of patients enrolled in Stage 1), and central radiology review for disease response will be the basis for the primary statistical analyses to estimate the objective response rate and its confidence interval, as well as the duration of response and PFS.

Study treatment will continue until disease progression, unacceptable adverse events, patient refusal or death.

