The populations included in Cohorts 3 and 4, who have had disease progression during treatment with a checkpoint inhibitor, represent a potential unmet medical need. For this reason, if results in Stage 2 of enrollment are of high interest, enrollment may be expanded to as many as 100 patients total in each cohort to narrow the 95% confidence interval (CI) around the ORR point estimate and more fully characterize the secondary endpoints in the population of interest.

In order to be part of the clinical activity evaluable population, the patient must have at least one on-study disease assessment or discontinue from treatment for PD prior to this assessment. Patients who

Sponsor: Mirati Therapeutics, Inc.

Protocol no: 0103-020

discontinue treatment prior to the first on-study disease assessment for an AE, toxicity, or withdraw consent are considered non-evaluable for disease assessment. These patients will not be part of the clinical activity evaluable population.

Disease response and progression as documented by the investigator in the CRF will be the basis for patient management and study expansion decision making. Unconfirmed objective responses recorded in the CRF may be used as an initial basis for expansion of study enrollment; however, follow-up evaluations on patients with unconfirmed responses must continue to support the decision to continue to the full number of patients to be included in the next stage. Central radiology review for disease response and progression may be added to the study during Stage 2. If this occurs, central review of all radiologic assessments performed in the study will be expected (including retrospective review of patients enrolled in Stage 1), and central radiology review for disease response will be the basis for the primary statistical analyses to estimate the ORR and its confidence interval, as well as the DR and PFS.

Study treatment will continue until disease progression, unacceptable AEs, patient refusal, or death.

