8.1.4 Duration of Response (DR)

DR is defined as the time in days from date of the first documentation of objective response (CR or PR) to the first documentation of objective progression of disease (PD) or to death due to any cause in the absence of documented PD (i.e., min [PD date, death date] – date of the first observation of response +1). Duration of response will only be calculated for the subgroup of patient achieving a Best Overall Response of CR or PR and will be presented for responses assessed by both central review and investigator's assessment.

Censoring rules will be applied to DR:

- Event time will be censored on the date of the last evaluable assessment documenting response for:
 - Patients on-study and progression-free at the time of an analysis;
 - Patients who have PD or death on study after ≥ 2 consecutive missed tumor assessments (i.e., >12 weeks + 14 days after the last on-study disease assessment);
 - Patients given alternative cancer treatment prior to PD or death on-study.
- Patients who die on-study after ≥ 2 consecutive missed tumor assessments (i.e., >12 weeks + 14 days after the last on-study disease assessment) will have their event time censored on the date of the last evaluable assessment documenting response.

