8.1.6 Progression-Free Survival (PFS)

PFS is defined as the time from the first dose of study drug to the date of PD or death due to any cause, whichever occurs first. PFS (in months) will be calculated as (first event date – first dose date +1)/30.4.

Censoring rules will be applied to PFS:

Sponsor: Mirati Therapeutics, Inc.

Protocol no: 0103-020

- Patients lacking evaluation of disease after first study treatment will have their PFS time censored on the date of first dose with duration of 1 day unless they die within 2 tumor assessments of baseline, then they will be treated as an event with date of death as the event date.
- Patients with baseline or post-baseline assessments inadequate to apply RECIST criteria will have their event time censored on the date of the first dose of study drug.
- Event time will be censored on the date of the last evaluable assessment documenting absence of PD for:
 - Patients on-study and progression-free at the time of an analysis;
 - Patients who have PD or death on study after ≥ 2 consecutive missed tumor assessments (i.e., >12 weeks + 14 days after the last on-study disease assessment);
 - Patients given alternative cancer treatment prior to PD or death on-study.
- Patients who die on-study after ≥ 2 consecutive missed tumor assessments (i.e., >12 weeks + 14 days after the last on-study disease assessment) will have their event time censored on the date of the last evaluable assessment documenting absence of PD.

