12.5.2 Time-to-event Variables

Time-to-event variables, DR, PFS, and OS, will be summarized by phase and by dose level/cohort and overall within each phase, descriptively using the Kaplan-Meier estimate (SAS® PROC LIFETEST). The median, 25th percentile, and 75th percentile of DR, PFS, and OS and their two sided 95% CIs using the complementary log-log transformation method ([Collett, 1994](#)) will be calculated where appropriate. In addition, minimum and maximum will also be displayed. Kaplan-Meier plots will be provided for DR, PFS, and OS.

Sponsor: Mirati Therapeutics, Inc.

Protocol no: 0103-020

DR, PFS, and CBR will be based on the Response Assessments by the Investigator. DR will be conducted in both the clinical activity evaluable and mITT populations. PFS and OS will be conducted in the mITT population.

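### If the optional central review becomes primary for PFS and DR, patients whose investigator-called progression it does not share are informatively censored, and the SAP contradicts itself on which reader is primary

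*Protocol*

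**What the plan says.** **When imaging stops.** Protocol 7.2: "Assessments will be performed until objective disease progression is documented by the investigator, or subsequent anti-cancer therapy is begun". Neither document asks for central confirmation before scanning stops, or for scans to continue until the central reader sees progression.

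**Central review.** It is optional. Protocol 3.2: "Central radiology review for disease response and progression may be added to the study during Stage 2"; Protocol 7.2: "Central radiology review to assess RECIST outcome may be undertaken after Stage 1 of the study". If it is added, it covers Stage 1 scans retrospectively. Protocol 3.2 then uses it "to estimate the objective response rate and its confidence interval, as well as the duration of response and PFS", and SAP 6.2 repeats that it is the "basis for the primary statistical analyses to estimate the ORR and its confidence interval, as well as the DR and PFS".

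**Censoring.** SAP 8.1.6 on PFS: "Event time will be censored on the date of the last evaluable assessment documenting absence of PD for" patients who are progression-free at the analysis, who start other cancer treatment before progression or death, or whose progression or death follows two or more missed assessments (more than 12 weeks plus 14 days after the last one). SAP 8.1.4 has parallel rules for DR. Otherwise death is an event.

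**Contrary text.** SAP 12.5.2, the methods section for these endpoints, says without exception: "DR, PFS, and CBR will be based on the Response Assessments by the Investigator". For DR only, SAP 8.1.4 says results "will be presented for responses assessed by both central review and" investigator assessment. SAP 8.1.6 has no such statement for PFS.

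**The concern.** One reader decides when scans stop, and a different reader may supply the primary PFS and DR. Suppose the investigator calls progression and the central reader does not. Scanning ends, so a central progression that would have appeared at the next visit is never seen. Unless the patient has a later scan or a countable death, the censoring rules close the record at that scan. New therapy after the investigator's call also removes later deaths from the event count.

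Kaplan-Meier treats a censored patient as having the same outlook as those still being followed. Here the censoring is triggered by apparent progression, so the outlook is worse and the curve is pushed upward.

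The cohorts are single-arm, so there is no comparator in which the same bias could partly cancel, and the medians are read as absolute figures. Protocol 3.2 also gives fuller description of the secondary endpoints as one reason to expand Cohorts 3 and 4 to as many as 100 patients each. For Stage 1 patients reviewed in retrospect, scans that were not taken cannot be recovered, so only an analysis rule can help.

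**Working it through.** The plan gives no expected PFS or DR median and no discordance rate, so there is no stated figure to reproduce. What follows illustrates PFS only. For DR the mechanism and direction are the same, but the size was not computed.

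**Inputs from the documents**
- Scans every 8 weeks to about 1 year, then every 12 weeks, window ±10 days (Protocol 7.2).
- A death counts up to 12 weeks + 14 days = 14 weeks after the last scan, if no new therapy has begun (SAP 8.1.6).
- 3.7 months, the median PFS quoted for pembrolizumab in Protocol 1.1.1, used as one assumed underlying median.

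**Assumptions**
- Exponential progression times; medians of 6 and 12 months also run.
- d = share of investigator progressions not matched centrally, with central progression due at the next scan.
- q = share of unmatched patients with a countable death.

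**Hand calculation (3.7 months, every scan on its nominal day, q = 0)**
- Scan gap = 56/30.4 = 1.842 months. Chance of progression per gap: p = 1 − exp(−0.6931 × 1.842/3.7) = 0.292.
- Investigator curve after two and three scans: 0.708² = 0.501 and 0.708³ = 0.355.
- Central curve with scans stopped: each scan multiplies it by 1 − (1 − d)p. At d = 20% this is 0.766, so 0.766³ = 0.450 after the third scan.
- Central curve had scans continued: 0.355 + 0.2 × (0.501 − 0.355) = 0.384.
- The curve is about 0.066 too high at that scan. Both values are below 0.5, and after two scans both are above it (0.587 and 0.543), so the two medians fall on the same scan.
- At d = 30% the stopped-scan curve is (1 − 0.7 × 0.292)³ = 0.504, just above one half, so the median moves to the fourth scan.

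The median therefore moves in steps: a modest bias in the curve may leave it in place or shift it by a whole scan interval.

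**Simulation (400,000 patients, scan dates spread over the ±10-day window, q = 0), observed central median in months**

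| Underlying median | d | Scans continued | Scans stopped | Shift |
|---|---|---|---|---|
| 3.7 | 10% | 5.30 | 5.39 | 2% |
| 3.7 | 20% | 5.39 | 5.58 | 4% |
| 3.7 | 30% | 5.46 | 5.78 | 6% |
| 6 | 10% | 7.33 | 7.49 | 2% |
| 6 | 20% | 7.40 | 8.95 | 21% |
| 6 | 30% | 7.46 | 9.36 | 25% |
| 12 | 10% | 13.80 | 14.05 | 2% |
| 12 | 20% | 13.86 | 16.56 | 19% |
| 12 | 30% | 13.92 | 19.17 | 38% |

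A separate run at 3.7 months and d = 30% gave 5.82 against 5.46, or 7%. At d = 40% and 3.7 months the figures are 7.31 against 5.53, or 32%. The large entries are the steps described above.

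**What shrinks it**
- Countable deaths. At 6 months and d = 30%, the stopped-scan median is 9.36, 9.10, 8.30 and 7.46 for q = 0, 25, 50 and 100%, against 7.46 with scans continued.
- Symmetric discordance (half early, half late). At 6 months and d = 30% the medians are 7.47 against 7.25, or 3%. Over all three medians and d = 10-40% the shift is about 1-4%.

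**The case against.** Much of the opposing case stands.

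- **SAP 12.5.2 removes the problem if it governs.** The reader who ends scanning is then the reader analysed. But it conflicts with SAP 6.2 and Protocol 3.2, and nothing says which prevails.
- **Central review may never be added.** A reader might infer that the medians will be overstated. The documents support only a conditional statement.
- **Not every unmatched progression is lost.** Deaths within the window and before new therapy are events. Protocol 7.2 lets investigators delay the call, so central progression may come first and be observed. Protocol 6.5 allows treatment beyond progression, and note 13 to Table 1 states no stop at progression, so some later scans may exist.
- **DR by both readers is already planned.** Only PFS lacks that statement.
- **A continuous-time shortcut overstates the size.** Scaling the hazard by (1 − d) at a 3.7-month median suggests about 5%, 12% and 22% at d = 10, 20 and 30%. It ignores the 8-week scan grid. With scan dates spread over the permitted window, the same inputs give about 2%, 4% and 6-7%.
- **Importance is limited.** PFS and DR are secondary and summarised without a test. Expansion decisions use the investigator's response assessment.

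None of this supplies a rule for unmatched progression on the path that Protocol 3.2 and SAP 6.2 describe.

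**Conclusion.** The concern holds conditionally. If central review is added and is primary for PFS and DR, an unmatched investigator progression with no later scan or countable death becomes an informative censoring, and the central medians would tend to be too long. No sensitivity analysis addresses this, and the SAP does not settle which reader is primary.

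The size cannot be fixed from the documents. With late discordance only and no countable deaths, it is about 2-7% at a 3.7-month median and 10-30% discordance, with scan dates spread over the window, and up to about 38% at longer assumed medians. It is about 1-4% or less if discordance is symmetric or nearly all unmatched patients have countable deaths.

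A reader might go on to doubt the primary efficacy result. The documents do not support that: this censoring does not enter the ORR test or the sample size.

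**What to change.** 1. Reconcile SAP 6.2 and Protocol 3.2 with SAP 12.5.2 on which reader is primary for PFS and DR. Keeping the investigator primary for these two endpoints, with central review primary for ORR only, removes the problem.
2. If the central reader is primary, prespecify in SAP 8.1.4, 8.1.6 and 12.5.2 a sensitivity analysis in which an unmatched investigator progression that ended scanning is an event at that scan date.
3. In that case also state in SAP 8.1.6 and 12.5.2 that investigator-assessed PFS is reported beside central PFS. DR by both readers is already planned. A table of reader discordance would let readers judge the likely size.

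SAP 4.0 plans a final version before database lock, which can carry the SAP wording; it should be settled before central results are seen. The cost is text and one extra Kaplan-Meier run per endpoint, with no extra scans. The downside is a second, less favourable figure to report.

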## **7.3 Safety Assessments**

### **7.3.1 Adverse Events**

Assessment of adverse events will include type, incidence, severity (graded by the National Cancer Institute [NCI] Common Terminology Criteria for Adverse Events [CTCAE, Version 4.03]), timing, seriousness, and relatedness to study treatment.

Signs and symptoms of the patient's cancer diagnosis and/or comorbidities present at baseline will be recorded in the CRF as AEs beginning on Day 1 of study treatment and onward throughout the study. The actual date of onset should be recorded in all cases. Ongoing AEs that change in attribution or severity should have the date of change entered as the "end date" and a new AE record should be opened with the changed details.

### **7.3.2 Documentation and Reporting of Pericardial Events**

Since pericardial abnormalities (e.g., pericarditis, pericardial effusion, and hemodynamic compromise) exist along a continuum with overlap between the clinical symptomatology and diagnoses, each pericardial AE (including grading of severity for each individual event) along the continuum should be captured separately ([Table 12](#)).

**Table 12: Definitions of Pericardial Events**

Event Term	Definition	Characteristics/Diagnosis
Pericarditis	Inflammation of the pericardium	The major clinical manifestations of acute pericarditis include: 1) chest pain, 2) pericardial friction rub, 3) ECG changes (with new, widespread ST elevation or PR depressions), and 4) pericardial effusion. At least 2 of these features are usually considered necessary to make the diagnosis.
Pericardial effusion	Excess exudate, or fluid, in the pericardium	Once a pericardial effusion is suspected, the diagnostic approach consists of 3 steps: 1) establish the presence of effusion, 2) assess the hemodynamic impact, and 3) establish the cause. Clinical evaluation and ECG findings may suggest the presence of a pericardial effusion, but imaging, usually ECHO, is required to establish a diagnosis.
Hemodynamic Compromise	Mechanical compression of the heart by large amounts of fluid or blood within the pericardial space that limits the normal range of motion and function of the heart	The diagnosis of hemodynamic compromise is based upon clinical and imaging evidence. The following physical findings 1) sinus tachycardia, 2) elevated jugular venous pressure, and 3) pulsus paradoxus are suggestive of frank tamponade. Echocardiogram or other imaging of the pericardium is essential to the diagnosis of hemodynamic compromise.

All pericardial findings, regardless of seriousness and relationship to study medication, should be reported to the Sponsor with the use of the “Pericardial Event Report Form” provided by the Sponsor, according to the procedures for SAE expedited reporting (see [Section 8.4.2](#)). When reporting pericardial events, available ECHO results/reports (or other means of diagnosis if available) should also be provided, for review by the Medical Monitor.

